5.2. Covariates

The primary analysis method is inverse probability of treatment weighting (IPTW) based on the individual propensity score (PS). Variables needed for the PS estimation include age, race, practice type, ECOG performance score, disease stage at initial diagnosis, visceral metastasis, number of disease sites, disease free interval, and comorbidities. The selection of these covariates for analysis are based on the study team's clinical judgment.

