4. ABSTRACT

Title: Real-World Treatment Effectiveness of Palbociclib in Combination With an Aromatase Inhibitor as 1st line Therapy in Metastatic Breast Cancer

Date of Abstract: 6 August 2021

Version: DRAFT version 2.0

Name and affiliation of the main author:

PPD , MD, PhD

PPD

Rationale and Background:

Palbociclib is an oral CDK4/6 inhibitor, approved for the treatment of adult patients with HR+/HER2- advanced or metastatic breast cancer (MBC) in combination with (1) an aromatase inhibitor as initial endocrine-based therapy in postmenopausal women or in men; or (2) fulvestrant in patients with disease progression following endocrine therapy. Since its approval in February 2015, palbociclib has rapidly become a standard-of-care in the treatment of HR+/HER2- MBC.

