7. RATIONALE AND BACKGROUND

According to American Cancer Society, breast cancer is the most common cancer in women and the second leading cause of cancer deaths (only lung cancer kills more women each year)¹. In the US, there will be an estimated 281,550 new cases of invasive breast cancer in women, 2,650 cases in men and 44,130 patients are estimated to die from breast cancer in 2021¹. In 2017, it was estimated that 154,794 women were living with metastatic BC in the US; of these 3 out of 4 progressed from an early stage BC²⁰. Metastatic breast cancer remains an incurable disease with 5-year survival rates of 28%¹. Hormone receptor-positive (HR+) breast cancer is the most commonly diagnosed subtype (~70-80%)²¹. The goal of treatment for MBC is to prolong the time to disease progression or extend life to the extent possible or improve/maintain quality of life of that survival².

Palbociclib, an oral CDK4/6 inhibitor, is approved for HR+/HER2- advanced and metastatic breast cancer in combination with an aromatase inhibitor or fulvestrant. Palbociclib is approved in the US based on improved median PFS demonstrated in 3 pivotal clinical trials: PALOMA-1 and PALOMA 2 (initial endocrine-based therapy in combination with letrozole for advanced disease) and PALOMA-3 (in combination with fulvestrant after progression on or after prior endocrine therapy). Approval was first granted based on findings from the Phase 2 PALOMA-1 trial³ in February 2015.

Palbociclib in combination with fulvestrant was approved 1 year later (February 2016) in pre or postmenopausal women with disease progression following endocrine therapy based on results from the phase 3 PALOMA-3 trial.²² Final OS data from that study has been reported.⁶ demonstrating median of 34.9 months versus 28 months in the palbociclib +

fulvestrant group versus fulvestrant alone (HR 0.81; 95% CI; 0.64, 1.03; 1-sided p=0.0249), which was not statistically significant.

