9.3. Variables

All variables are assessed or defined by Flatiron using business rules before and after Palbociclib + AI or AI alone initiation.

Variable	Operational definition
Demographic characteristics	
Age	Age at MBC diagnosis, years
Age category	<50, 50-64, 65 –74, ≥75 years
Index treatment year	2015, 2016, 2017, 2018, 2019, 2020
Gender	Male, female, unknown
Race	White, Black, Asian, other, unknown
Region of residence	Based on region where the patient resides: Northeast, Midwest,
	South, West
Practice type	Academic, community
Insurance type	Commercial, Medicare, Medicaid

Palbociclib (IBRANCE®) A5481151, NON-INTERVENTIONAL STUDY PROTOCOL Protocol Amendment 1, 16 Feb 2022

Management at the			
Menopause status	Pre or perimenopausal, postmenopausal, Unknown as defined by Flatiron.		
	Menopausal status was either assigned or abstracted,		
	depending on the patient's age at 1L start. The following		
	was used to determine menopausal status:		
	Patients age 60 years or older at 1L start date are		
	assigned as "postmenopausal".		
	• Patients younger than age 60 at 1L start underwent		
	abstraction for menopausal status and are categorized as		
	follows:		
	o If there was explicit documentation by the		
	clinician of the patient being "postmenopausal" or		
	patient was stated as being menopausal at a certain		
	age prior to the start of first-line therapy for		
	metastatic breast cancer, or implicit documentation		
	of "Prior Bilateral Salpingo-Oophorectomy (BSO)		
	with or without hysterectomy" prior to or within 30		
	days after the 1L start, the patient's menopausal		
	status was derived as "postmenopausal"		
	 If there was explicit documentation by the 		
	clinician of the patient being "premenopausal" or		
	implicit documentation of "Regular menses",		
	between the metastatic breast cancer diagnosis date		
	and up to 30 days following the start of first-line		
	therapy the patient's menopausal status was derived		
	as "premenopausal"		
	If there was explicit documentation by the		
	clinician of the patient being "perimenopausal"		
	between the metastatic breast cancer diagnosis date		
	and up to 30 days following the start of first-line		
	therapy the patient's menopausal status was derived		
	as perimenopausal		
	If there is no explicit or implicit documentation		
	of menopausal status prior to or within 30 days		
	1 1		
	after the 1L start, the patients were considered as		
	having "Unknown" menopausal status		

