9.7.4.1. Inverse probability treatment weighting (IPTW)

Inverse probability treatment weighting will be used to balance baseline demographic and clinical characteristics between comparison cohorts (for instance, palbociclib + AI versus AI alone) in statistical analyses³². Variables to be used in the computation of propensity scores (PS) required to perform IPTW include key baseline demographics (e.g. age, race, practice type) and clinical characteristics (e.g. ECOG performance score, disease stage at initial diagnosis, visceral metastasis, number of disease sites, disease free interval, and comorbidities). In the event that IPTW method does not balance potential confounder variables, analysis by PS quintiles will be used.

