5. ENDPOINTS AND COVARIATES

5.1. Efficacy/Effectiveness Endpoint(s)

Variable	Operational definition
Demographic characteristics	
Age	Age at MBC diagnosis, years
Age category	<50, 50-64, 65 –74, ≥75 years
Index treatment year	2015, 2016, 2017, 2018, 2019, 2020
Gender	Male, female, unknown
Race	White, Black, Asian, other, unknown
Region of residence	Based on region where the patient resides: Northeast, Midwest, South, West
Practice type	Academic, community
Insurance type	Commercial, Medicare, Medicaid
Menopause status	
Pre or perimenopausal, postmenopausal, Unknown as defined by Flatiron.
 
Menopausal status was either assigned or abstracted, depending on the patient's age at 1L start. The following was used to determine menopausal status:
 
 ● Patients age 60 years or older at 1L start date are assigned as "postmenopausal". ● Patients younger than age 60 at 1L start underwent abstraction for menopausal status and are categorized as follows: 
 ○ If there was explicit documentation by the clinician of the patient being "postmenopausal" or patient was stated as being menopausal at a certain age prior to the start of first-line therapy for metastatic breast cancer, or implicit documentation of "Prior Bilateral Salpingo-Oophorectomy (BSO) with or without hysterectomy" prior to or within 30 days after the 1L start, the patient's menopausal status was derived as "postmenopausal" ○ If there was explicit documentation by the clinician of the patient being "premenopausal" or implicit documentation of "Regular menses", between the metastatic breast cancer diagnosis date and up to 30 days following the start of first-line therapy the patient's menopausal status was derived as "premenopausal" ○ If there was explicit documentation by the clinician of the patient being "perimenopausal" between the metastatic breast cancer diagnosis date and up to 30 days following the start of first-line therapy the

PFIZER CONFIDENTIAL

Variable	Operational definition

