7. STATISTICAL METHODOLOGY AND STATISTICAL ANALYSES

7.1. Statistical methods

The inverse probability of treatment weighting (IPTW) technique will be used as the primary analysis method to control for confounders when comparing the cohorts. Propensity scores for use in IPTW will be calculated using a multivariable logistic regression model based on

PFIZER CONFIDENTIAL

the proposed baseline covariates in Section 5.2. Stabilized weights based on the propensity scores will be computed. The balance in important prognostic baseline characteristics will be assessed using a standardized differences approach, with values ≥ 0.10 indicating a non-negligible imbalance. After IPTW, no significant differences are expected among all pre-index measures between the patient cohorts, and the treatment effect that is calculated based on the weighted population is considered to be the true effect.

The Kaplan-Meier method adjusted by stabilized IPTW will be used to estimate median survival time and its 95% confidence intervals (CIs) for OS, rwPFS, and duration of treatment. Cox proportional models with a robust sandwich estimator adjusted by stabilized IPTW will be used to estimate hazard ratio and its 95% CIs for OS, rwPFS, and duration of treatment. The Cox model proportionality assumption will be evaluated by visually inspecting the Kaplan-Meier plot among the matched cohorts and confirmed by testing the significance of interactions between treatment modality and the log of time as well as each time-dependent covariate and the log of time. If the proportionality assumption is violated, an interaction term of time may be added.

OS and rwPFS rates at 12, 24, 36, 48, and 60 months will be estimated with corresponding 2-sided 95% CIs using the IPTW weighted Kaplan-Meier method.

Means, medians, and standard deviations will be provided for continuous variables when performing descriptive analysis of continuous data. Numbers and percentages will be provided for dichotomous and polychotomous variables when performing descriptive analysis of categorical data. Bivariate comparisons of baseline characteristics and outcomes measures will be provided. Appropriate tests (e.g., t-test, chi-square test) will be used based on the distribution of the measure. An unadjusted Kaplan Meier curve will be drawn to illustrate time-to-event.

All data analysis will be executed using statistical software SAS version 9.4 or later.

7.2. sensitivity analysis

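### Index treatment year is collected but is in no propensity-score list, so confounding of overall survival by calendar time is left uncontrolled; its size and direction cannot be derived from the documents

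*SAP*

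**What the plan says.** "Index treatment year" is listed among the demographic characteristics in Protocol 9.3 and again in SAP 5.1, with the levels "2015, 2016, 2017, 2018, 2019, 2020".

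The propensity-score covariates appear in three places, and none names index year:

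- SAP 5.2: "Variables needed for the PS estimation include age, race, practice type, ECOG performance score, disease stage at initial diagnosis, visceral metastasis", followed by "number of disease sites, disease free interval, and comorbidities".
- Protocol 9.7.4.1: an open-ended list that begins "key baseline demographics (e.g. age, race, practice type" and continues with clinical characteristics.
- Protocol section 4 (abstract), Data Analysis: a similar list given as examples.

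SAP 7.1 builds the logistic propensity model from "the proposed baseline covariates in Section 5.2". If weighting does not balance the cohorts, the protocol falls back to quintiles of the propensity score. Propensity-score matching is the one sensitivity analysis specified for control of confounding (Protocol 9.7.4.4, SAP 7.2). Neither names a different covariate set. Index year is also absent from the subgroup lists (Protocol 9.7.4.5, SAP 4.2) and from the limitations (Protocol 9.9).

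On timing, the index window runs from 03 February 2015 to 31 March 2020 (SAP 2.1). The abstract says "Since its approval in February 2015, palbociclib has rapidly become a standard-of-care in the treatment of HR+/HER2- MBC". Protocol section 7 dates the approval of palbociclib with fulvestrant to February 2016.

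**The concern.** A baseline variable confounds the comparison if it is related both to the treatment received and to the outcome.

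The first link follows from the documents. A drug approved in the month the window opens, which then became standard quickly and makes up about half of the cohort overall (Protocol 9.7.2 expects close to 1:1), must have had a rising share over the window. AI-alone patients will tend to have earlier index dates.

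The second link is plausible but only qualitatively supported. Treatment available after first line changed during the window, palbociclib with fulvestrant being the dated example. Patients indexed in different years may therefore have different survival for reasons unrelated to their first-line drug.

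If both links hold, part of any survival trend over calendar time is attributed to palbociclib in the primary HR. The three planned adjustments use the same score, so agreement between them would not be evidence against this.

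**Working it through.** **1. The plan's own scale.** Protocol 9.7.2 plans 750 deaths for HR 0.80, two-sided 0.05, 1:1. Schoenfeld: 4 × (1.960 + 0.842)² / (ln 0.80)² = 631 deaths for 80% power. At 750, power = Φ(√750/2 × 0.2231 − 1.960) = Φ(1.096) = 86.3%. So 750 is more than 80% power requires, and at least 80% is true. I use it only to scale the shifts: SE(log HR) ≈ 2/√750 = 0.073.

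**2. How much uptake must change to matter by the SAP's own criterion.** Assume uniform index dates over a window of length 1 and a share rising linearly by δ around 50%. The difference in mean index date is δ/3, and the within-arm variance is 1/12 − (δ/6)². The standardized difference is the ratio of δ/3 to the within-arm SD:

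- δ = 0.086 (45.7% to 54.3%): 0.10, the threshold in SAP 7.1
- δ = 0.40 (30% to 70%): 0.133/0.281 = 0.47
- δ = 0.60 (20% to 80%): 0.200/0.271 = 0.74

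A rise of about 9 percentage points is enough to fail the balance criterion, if index year is checked.

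**3. Effect on the HR.** Inputs from the documents: a window of 61.9 months, cutoff on 30 September 2020 (6 months after the last entry), and an AI-alone median of 40 months. Assumed inputs: uptake by index year, and a multiplicative hazard trend per index year centred on 2017. Each scenario has 1,000,000 simulated patients with exponential survival. Runs with flat 50% uptake gave 0.998 to 1.004 for a true 1.00, so simulation error is about 0.005.

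Cox HR with index year omitted, true HR 1.00:

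| Uptake, first to last year | Trend 0.90 | 0.95 | 1.00 | 1.05 |
|---|---|---|---|---|
| 40% to 60% | 0.978 | 0.986 | 1.001 | 1.017 |
| 30% to 70% | 0.946 | 0.969 | 0.999 | 1.025 |
| 20% to 80% | 0.917 | 0.960 | 1.002 | 1.040 |

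True HR 0.80:

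| Uptake, first to last year | Trend 0.90 | 0.95 | 1.00 | 1.05 |
|---|---|---|---|---|
| 40% to 60% | 0.778 | 0.790 | 0.799 | 0.815 |
| 30% to 70% | 0.760 | 0.779 | 0.798 | 0.814 |
| 20% to 80% | 0.732 | 0.773 | 0.799 | 0.828 |

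With stabilized weights that include index year, the estimates return to 0.995–1.006 and 0.791–0.805.

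**4. Against sampling error at 750 deaths.** An apparent 0.97 under the null is ln(0.97)/0.073 = −0.42 SE; 0.95 is −0.70 SE; the extreme 0.917 is −1.19 SE; 1.040 is +0.54 SE. The chance of falsely declaring benefit, nominally 2.5%, becomes Φ(−1.960 + 0.42) ≈ 6% at 0.97 and Φ(−1.960 + 0.70) ≈ 10% at 0.95.

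**5. Cost of including year.** Effective sample size is 98.5%, 93.9% and 85.0% for the three uptake patterns. Power at 750 deaths times these fractions is 85.8%, 84.1% and 80.4%.

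**The case against.** **No OS trend is shown.** The documents contain no survival by index year. With no trend the bias is nil at any uptake (the 1.00 column). This stands: a reader might infer that the OS comparison is confounded, but the documents support only that this confounder is not controlled.

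**The direction is an input.** A reader might also infer that the bias must favour palbociclib. That follows only from assuming a falling hazard; a rise of 5% per year reverses it.

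**The mechanism is thin.** Table 1 of the protocol lists other CDK4/6 inhibitors without dates. Protocol section 7 calls palbociclib the first approved of the class, which gives the order but not the timing. The one dated change, February 2016, falls about when a patient who started letrozole in February 2015 would reach the 11.9-month median real-world PFS quoted for letrozole alone. That option therefore varies little across most of the window. The steepest trend tested is also strong: at 0.90 per year the AI-alone median moves from 40 × 0.90² = 32.4 months (2015) to 40/0.90³ = 54.9 months (2020). This limits the likely size but does not remove the question.

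**The imbalance would probably be seen.** SAP 7.1 plans comparisons of baseline characteristics, and index year is listed among them. This is fair, but no stated method would then repair the imbalance, since quintiles of and matching on the same score omit year too.

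**Unequal follow-up is not itself a bias.** Potential follow-up differs by arm in the scenarios (30.1 v 42.8 months at 20% to 80% uptake, palbociclib + AI v AI alone). Different administrative censoring does not alone bias Kaplan-Meier or, under proportional hazards, Cox estimates. I claim no separate harm from it.

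**The covariate lists are open.** They are worded as examples or inclusions and rest on clinical judgment, and Protocol 9.9 disclaims causality. Year could be added without contradiction, but nothing commits to it, and SAP 7.1 points to the 5.2 list.

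**Conclusion.** The omission is exact, and nothing elsewhere in the two documents repairs it. Calendar time is tied to treatment by the documents' own account and is plausibly tied to OS, so confounding by calendar time is uncontrolled in all three planned propensity-score analyses.

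Size and direction cannot be derived. Within the assumed ranges (uptake of 20% to 80% or narrower, hazard trend 0.90 to 1.05 per index year), a true HR of 1.00 appears as about 0.92 to 1.04 and a true 0.80 as about 0.73 to 0.83. In no scenario did calendar time alone turn a null effect into 0.80. Under a 5% yearly fall the shift is about half an SE or less at 750 deaths; only the steepest combination exceeds one.

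These results use the September 2020 cutoff given in Protocol 9.2.1 and the SAP. Protocol 9.1 gives 30 September 2021, and the two must be reconciled. The point is an inexpensive improvement to the primary analysis, not a demonstration that its result would be wrong.

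**What to change.** - Add index treatment year, with the six levels already defined, to the propensity model in SAP 5.2 and Protocol 9.7.4.1. State that the quintile fallback and the matching use the same model.
- Name index year in the standardized-difference check (threshold 0.10).
- Tabulate treatment by index year.
- Report the primary OS HR with and without index year in the score.

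The cost is one collected covariate and a sentence or two in each document. Weights become more variable, with an effective sample size of about 85% to 98% in the assumed scenarios and power still at least 80.4% at 750 deaths.

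There is one further downside. If year strongly predicts treatment but barely affects OS, including it can amplify residual unmeasured confounding. A main effect for year also does not remove any change over time in which patients are given AI alone. The paired HRs would help show how much the choice matters.

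Protocol section 6 planned the primary analysis to start on 01 September 2021. If it has already been run, the version with index year should be labelled as added afterwards.

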Variables: Variables will be obtained from both structured and unstructured data using Flatiron's technology-enabled data processing. The following variables will be included for the analyses: demographics (e.g., age, race, menopausal status, region), baseline clinical characteristics (e.g., date of initial BC diagnosis, date of MBC diagnosis, endocrine sensitivity, ECOG performance status, disease stage at initial diagnosis, site of metastasis, and number of disease sites), treatment patterns (e.g., AI therapy partner, starting dose, dose adjustment, duration of treatment, discontinuation, reasons for discontinuation, time to subsequent therapy, and time to chemotherapy), and effectiveness outcomes (i.e., OS, rwPFS, rwPFS2, rwTR).

Data source:

The Flatiron Health Analytic Database is a nationwide longitudinal, demographically, and geographically diverse de-identified database derived from electronic health record (EHR) data in the US. The Flatiron Health EHR-derived database includes structured and unstructured data from over 280 cancer clinics (~800 sites of care) representing more than 2.4 million US cancer patients available for analysis (see Section 9.4 for a more detailed description of the Flatiron Health Analytic Database).

Study Size: Based on an initial feasibility assessment using Flatiron Health Analytic Database between February 2015 – February 2020, there are over 1,500 patients in the database with HR+/HER2- MBC who received palbociclib + AI and AI alone as first line therapy for their metastatic disease, respectively. Of these, ~200 patients are thought likely to be pre/perimenopausal based on age at metastatic diagnosis. All patients who meet inclusion and exclusion criteria will be included in the statistical analyses.

Data Analysis:

The primary effectiveness endpoint (i.e., OS) of palbociclib + AI versus AI alone will be compared by weighted log-rank tests based on the IPTW approach. The method of IPTW will be the initial method used to address the potential effects of observed confounders. Participant characteristics such as age, race, practice type, ECOG performance score, disease stage at initial diagnosis, visceral metastasis, number of disease sites, endocrine sensitivity, and comorbidities will be examined for unequal baseline distributions. These variables will

Palbociclib (IBRANCE®) A5481151, NON-INTERVENTIONAL STUDY PROTOCOL Protocol Amendment 1, 16 Feb 2022

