be used to compute a propensity-to-treatment score (PS) by a logistic regression model, where the outcome variable is being in the palbociclib + AI group (yes, no). The individual PS is used to obtain the individual IPTW which is applied to the observations to assess the balance between treatment arms in the potential confounders after weighting.

If the method of IPTW yields balanced treatment groups with respect to the potentially measured confounders, then a weighted log-rank test using IPTW will be used to compare OS between the palbociclib + AI group and the AI alone group, with a nominal p< 0.05, two-sided, indicating an OS benefit in the palbociclib + AI group. The weighted Cox proportional hazards model will be used to compute the hazard ratio and the corresponding 95% CI. If the method of IPTW does not yield balanced treatment groups with respect to the potential confounders, analysis by PS quintiles will be used. All subjects will be stratified in quintiles based on the PS. A stratified log-rank test (stratified by PS quintiles) will be used to compare OS between the palbociclib + AI group and the AI alone group, with a nominal p< 0.05, two-sided, indicating an OS benefit in the palbociclib + AI group. This method allows for the comparison of subjects with similar PS without the potential loss of subjects in 1-1 matching. A stratified Cox proportional hazards model (stratified by PS quintiles) will be used to compute the hazard ratio and the corresponding 95%CI.

These time-to-event endpoints will also be summarized using the weighted Kaplan-Meier method and displayed graphically where appropriate. Similar analyses will be performed for rwPFS. Logistic regression analysis will be performed to compare rwTR between the 2 treatment groups. Descriptive analyses will be performed to report baseline patient demographics and clinical characteristics, treatment patterns, and time to next line of systemic anticancer therapy from palbociclib + AI initiation. Subgroup analyses will be conducted according to age, ethnicity, ECOG performance, metastatic site (i.e. visceral, bone only, etc.), and endocrine sensitivity as sample sizes allow.

A detailed statistical analysis plan (SAP) will be developed separately.

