The pre-specified analysis of patients who were endocrine sensitive demonstrated an OS HR of 0.72; 95% CI: 0.55, 0.94 in those without sensitivity to previous endocrine treatment (HR of 1.14; 95% CI; 0.71, 1.84). The Phase 3 PALOMA-2 study confirmed the findings from the PALOMA-1 trial, demonstrating a median PFS in the palbociclib + letrozole arm of 24.8 months compared to 14.5 months in the placebo + letrozole arm (HR of 0.58; 95% CI: 0.46, 0.72; 1-sided p<0.001)⁵. With extended follow-up, the median PFS was 27.6 vs 14.5 months; P<0.0001; data cutoff: May 31, 2017)⁴. Subgroup PFS analyses according to stratification factors and demographic characteristics or prognostic factors revealed consistent results in PALOMA-2⁵ and PALOMA-3 trial^{22, 23} in all studied subgroups. Results for the secondary endpoint of OS data from PALOMA-2 are event driven and not yet available.

Of note, a patient population *not* included in the PALOMA-1 or -2 trials investigating palbociclib + letrozole as first line treatment for women with ER+/HER2- advanced disease was the pre or perimenopausal population. The PALOMA-3 study investigating palbociclib + fulvestrant did include pre or perimenopausal patients, however the study evaluated patients who were progressed following endocrine therapy. The subgroup of 108 pre or perimenopausal women (out of the total 521) randomized to palbociclib + fulvestrant + goserelin versus placebo + fulvestrant + goserelin in a 2:1 fashion showed a statistically longer median PFS of 9.5 versus 5.6 months respectively (HR of 0.50; 95% CI: 0.29, 0.87)²⁴. The safety profile from the PALOMA-2 and -3 trials were consistent, with no new safety signals identified across the Phase 3 studies. Long-term pooled safety analyses of the 3 randomized Phase 2 and 3 studies demonstrated no evidence of specific cumulative or delayed toxicities with palbociclib + endocrine therapy.²⁵ The primary toxicity of palbociclib is neutropenia, which can be managed with dosing interruption and/or dose reduction.

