9.7. Statistical considerations and data analysis

Detailed methodology for summary and statistical analyses of the data collected in this study are outlined here and further detailed in a statistical analysis plan (SAP). The SAP may

modify what is outlined in the protocol where appropriate; however, any major modifications of the primary endpoint definitions or their analyses will also be reflected in a protocol amendment.

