9.7.2. Sample size determination

Approximately 3000 patients will be included with close to a 1:1 ratio between palbociclib + AI and AI alone cohorts. The median OS for AI alone is assumed to be 40 months. An improvement of 25% to a median OS of 50 months (corresponding to a hazard ratio of 0.80) would be considered clinically meaningful. Therefore, 750 OS events will be required to have at least 80% power to detect a hazard ratio of 0.80 using a two-sided log-rank test at a significance level of 0.05 based on the exponential distribution assumptions of OS for both cohorts.

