9.9. Limitations of the research methods

Given the retrospective nature of the study, some limitations are present including those typical of a data source where the primary purpose for collection was other than research. These include potential bias in treatment selection, incomplete or missing data, limited data on comorbidities, potential for inaccurate data capture, lack of scheduled assessments and lack of standardized assessment of tumor response or progression free survival. In addition, response to treatment and disease progression were determined based on the individual treating physician's clinical assessment or interpretation of radiographic scans or pathology results rather than a standard criterion such as RECIST.

Although IPTW will be used to balance patient characteristics and sensitivity analyses (e.g., PSM) will be conducted, other variables unavailable in the database, such as disease-free interval and prior therapy in neoadjuvant setting cannot be statistically controlled. Sample size may not be large enough for some subgroup analyses. Additionally, no causality could be made from the retrospective analysis. Moreover, these findings may not be generalizable to other patient populations.

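### The primary OS propensity score leaves out endocrine sensitivity, which the abstract includes, and uses instead a disease-free interval that is undefined and that the protocol calls unavailable

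*SAP*

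**What the plan says.** Three places list covariates for the propensity score.

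- **Protocol abstract, Data Analysis.** The list includes "visceral metastasis, number of disease sites, endocrine sensitivity, and comorbidities will be examined for unequal baseline distributions. These variables will" "be used to compute a propensity-to-treatment score (PS) by a logistic regression model". Endocrine sensitivity is therefore both a score covariate and a characteristic checked for balance.
- **Protocol 9.7.4.1.** Disease-free interval stands where endocrine sensitivity stood in the abstract.
- **SAP 5.2.** The same as 9.7.4.1: "visceral metastasis, number of disease sites, disease free interval, and comorbidities".

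Protocol 9.7 allows the SAP to "modify what is outlined in the protocol where appropriate", and SAP 7.1 fits the logistic model on the Section 5.2 covariates. The SAP list is therefore the working specification.

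Protocol 9.9 then names among the study's limitations "other variables unavailable in the database, such as disease-free interval and prior therapy in neoadjuvant setting cannot be statistically controlled".

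Endocrine sensitivity has a full definition, with sensitive, resistant and unknown levels, in protocol 9.3 and SAP 5.1. Protocol 7 and SAP 2 describe it as new for this study, and it is a planned subgroup factor (protocol 9.7.4.5, SAP 4.2). Disease-free interval appears in the protocol's abbreviation list but has no row in either variable table. The nearest defined variable is the number of months between the initial and the metastatic diagnosis. Neither document says that this is the disease-free interval.

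**The concern.** In a non-randomised comparison the covariate list determines the primary estimate. SAP 7.1 goes as far as to treat the weighted effect as the true one. Two things go wrong if the SAP list is followed literally.

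First, the model may not be reproducible. Two analysts could reasonably build different weights: one using the interval between diagnoses, the other dropping disease-free interval because protocol 9.9 says it is unavailable. No text says how the interval enters the score for de novo patients, for whom it is near zero. No text says what happens when a date is missing, and SAP 6 rules out imputation.

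Second, endocrine sensitivity is not adjusted for, although the abstract says it is. The protocol treats it as relevant to OS: "The pre-specified analysis of patients who were endocrine sensitive demonstrated an OS HR of 0.72", against 1.14 in patients without sensitivity. Those are treatment effects within subgroups of a later-line trial. They do not measure how prognostic the variable is here, or how it influenced the choice of treatment.

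The planned back-ups share the gap. In the fallback, "All subjects will be stratified in quintiles based on the PS", and the matching analysis in SAP 7.2 also rests on a propensity score. The SAP gives no other covariate list for either. A subgroup analysis by endocrine sensitivity could expose the problem but would not correct the overall hazard ratio.

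**Working it through.** **Comparison of the lists**

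| Covariate | Abstract | Protocol 9.7.4.1 | SAP 5.2 |
|---|---|---|---|
| Age, race, practice type, ECOG, initial stage, visceral disease, number of sites, comorbidities (8) | yes | yes | yes |
| Endocrine sensitivity | yes | no | no |
| Disease-free interval | no | yes | yes |

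Eight covariates are shared and one is swapped. Protocol 9.7.4.1 and SAP 5.2 do not differ from each other. The covariate that was dropped is defined and collected. The one that replaced it is undefined and, by protocol 9.9, unavailable.

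**How far the listed covariates stand in for endocrine sensitivity**

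All patients who are stage IV at initial diagnosis are sensitive by definition, so initial stage captures that part. Among recurrent patients the class depends on whether endocrine therapy was given and on when progression occurred relative to its completion. Neither stage nor the interval between diagnoses records that, so the adjustment is partial at best.

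**Illustrative size (assumed inputs)**

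The plan gives no figure for this point and the documents give no prevalence, prognostic effect or selection effect. The assumptions are:

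- de novo share 0.3 or 0.4;
- resistant share of recurrent patients 0.3 or 0.5;
- probability of palbociclib 0.5 in de novo patients and 0.5 overall in recurrent patients, so weighting on de novo status changes nothing;
- odds ratio (OR) of receiving palbociclib, resistant versus sensitive recurrent patients, 0.67, 0.80, 1.25 or 1.5;
- prognostic hazard ratio of resistance, h = 1.3, 1.5 or 2.0;
- no disease-free interval in the score.

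Worked case: de novo 0.3, resistant 0.5 of recurrent, OR 1.5, h = 2.

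1. Resistant share overall: 0.7 × 0.5 = 0.35.
2. Probability of palbociclib: 0.5505 if resistant, 0.4495 if sensitive. These average 0.5 and give an odds ratio of 1.5.
3. Resistant share by arm: p1 = 0.35 × 0.5505 / 0.5 = 0.385 (palbociclib + AI); p0 = 0.35 × 0.4495 / 0.5 = 0.315 (AI alone).
4. Standardised difference: (p1 − p0) / √[(p1(1 − p1) + p0(1 − p0)) / 2] = 0.0707 / 0.476 = 0.149.
5. Approximate hazard ratio multiplier: (1 + (h − 1)p1) / (1 + (h − 1)p0) = 1.385 / 1.315 = 1.054. A true 0.80 would read 0.843.
6. Standard error of the log hazard ratio at the planned 750 deaths, 1:1, ignoring weighting: 2/√750 = 0.073. The shift is ln(1.054) / 0.073 = 0.72 standard errors.

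All settings:

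| OR | Absolute standardised difference | Multiplier | 0.80 reads as |
|---|---|---|---|
| 0.67 | 0.131–0.147 | 0.950–0.986 | 0.760–0.789 |
| 0.80 | 0.073–0.082 | 0.972–0.992 | 0.777–0.794 |
| 1.25 | 0.073–0.082 | 1.008–1.029 | 0.806–0.823 |
| 1.5 | 0.133–0.149 | 1.015–1.054 | 0.812–0.843 |

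The resistant share differs between arms by 3 to 7 percentage points. The SAP's 0.10 limit is reached only at an odds ratio of about 0.74–0.76 or 1.31–1.36, depending on prevalence. An imbalance of this kind could therefore pass or fail the check, provided endocrine sensitivity is checked at all.

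**The case against.** The abstract is the outlier. The protocol body and the SAP agree, the SAP may modify the protocol, and SAP 5.2 says the covariates were chosen on clinical judgement, so the swap may be deliberate. The protocol lists are also worded as examples. This stands in part: the documents do not settle what was intended. But they give no reason for the swap, SAP 7.1 ties the model to Section 5.2, and the right to modify the protocol does not make an unavailable variable available.

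Disease-free interval may simply mean the interval between diagnoses, and 9.9 may be the sentence in error. That is quite possible. De novo patients would then also be identified by stage, which is already in the score. It still has to be written down, because at present 9.9 contradicts it.

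SAP 7.1 expects no significant differences after weighting on any pre-index measure and plans bivariate baseline comparisons, so a careful analyst would probably look at endocrine sensitivity. That is fair, but it is an expectation and not a named list, and noticing an imbalance does not put the variable in the score.

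The subgroup hazard ratios of 0.72 and 1.14 suggest effect modification and do not show confounding. This stands, and they carry no weight in the size estimate. The illustration also takes the less favourable reading, with no disease-free interval in the score. A usable interval would be expected to shrink the shift.

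**Conclusion.** The concern holds. The primary weights, built as SAP 5.2 and 7.1 direct, leave out a defined baseline covariate that the abstract says is in the score, and require one that has no definition and that protocol 9.9 says cannot be used. This is a conflict in the specification of the primary model and not just missing detail.

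Confidence is high on the textual conflict and does not extend to the bias. Residual confounding by endocrine sensitivity would be partial, and its size and direction cannot be derived from the documents. The assumed settings give a modest shift in either direction, below one standard error throughout. The case for change rests on the contradiction and the low cost of repair, not on those figures. It should be corrected.

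**What to change.** 1. Add endocrine sensitivity (sensitive, resistant, unknown) to the score in SAP 5.2 and protocol 9.7.4.1, as the abstract already states. The unknown level allows it to enter without imputation.
2. Either define disease-free interval from the recorded diagnosis dates, with a rule for de novo patients and one for missing dates, and correct protocol 9.9; or remove it from the score.
3. Use one identical covariate list in the abstract, protocol 9.7.4.1 and SAP 5.2, and make 9.9 agree with it.
4. Name the balance variables in SAP 7.1 by carrying over the abstract's list, endocrine sensitivity included, for the 0.10 standardised-difference check.

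The cost is wording in two documents. Endocrine sensitivity and the diagnosis dates are already collected, so no new data are needed. One more covariate may make the weights slightly more variable.
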